12.2.2 Post-Surgery

Following the conclusion of the surgery procedure, the surgeon will complete a short paper questionnaire for each breast surgery technique, refer to section 26.2, appendix 2: Surgeon Questionnaire.

The study team will record the patient-reported pain scores in both breasts at 18 hours (+/- 2 hours) post-surgery.

Patient will be asked to complete Modules 7, 9 and 14 of the BREAST-Q Version 2.0© Reconstruction questionnaire at their last follow up visit.

12.3 Adverse Event Monitoring and Management

Patients experiencing adverse events while in the study will be managed according to local guidelines. Any adverse reactions to the fluorescent Indocyanine Green (ICG) dye will be reported according to local procedures.

This study is a non-interventional study. No routine adverse event reporting will be undertaken as part of this protocol.

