10.2 Secondary Endpoints

To compare the following post-surgical outcomes, as associated with the breast where the retractor technique is used during surgery versus the breast where the non-retractor technique is used, within the first 30 days post-surgery:

• Patient hospital re-admission, where applicable Perf-Act BreCon Protocol Version Number: 1.1 Version Date: 18/ Dec/ 2023

- Patient hospital stay duration, where applicable
- Patient re-operation required, where applicable
- Patient-reported post-surgery pain scores assessed at the following time points: 18 hours, follow-up week 1, week 2 and week 4-6
- Incidence, type and severity of surgery-related adverse events, where applicable

Comparison of patient's pre- and post-surgery outcomes as measured by Modules 7, 8, 9 and 14 of the BREAST-Q Recon version 2.0 questionnaire.

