12 PROCEDURES AND ASSESSMENTS

Refer to Section 26.1: Appendix 1 for Schedule of Assessments.

Patients will be clinically assessed throughout the study as per local practice.

Clinical assessments may be done remotely by telephone or videoconferencing, as appropriate and as per local practice.

Surgery-related adverse events will be recorded at each clinic visit from the point of surgery until the end of the 30-day follow-up period.

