- TR1- beginning of mastectomy procedure, defined as pre-incision on table
- TR2- when the surgeon switches from finger dissection technique to metal retractors
- TR3- end of mastectomy, defined as post-mastectomy before wound closure

At each time point (TR1, TR2 & TR3), two tissue perfusion relative values (%) and the time in HH: MM (24hr format) will be taken and recorded. The first value will be the worst tissue perfusion relative value (%) observed in the 10x10cm area surrounding the incision, and the second value will be the best tissue perfusion relative value (%) observed anywhere in the breast.

Left Breast (Retractor Technique)

The operating surgeon will then conduct the mastectomy procedure in the left breast using metal retractors **only** from the beginning until the end of the procedure.

The surgeon will request that the ICG dye be administered to the patient, after confirming the fluorescent imager is ready to use, working and in hand at the following three time points:

- TL1- beginning of mastectomy procedure, defined as pre-incision on table
- **TL2** at the same time point that the surgeon switched from using fingers to metal retractors in the right breast (Time in mins = Right breast TR2 –Right breastTR1)

For example: If surgeon switched from the non-surgical (finger dissection) technique to retractors after 30 minutes in the right breast, then the tissue perfusion measurements in the left breast at time point TL2 will be taken 30 minutes after the beginning of the mastectomy procedure TL1 in the left breast.

• TL3- end of mastectomy, defined as post-mastectomy before wound closure

At each time point (TL1, TL2 & TL3), two tissue perfusion relative values (%) and the time in HH: MM (24hr format) will be taken and recorded. The first value will be the worst tissue perfusion relative value (%) observed in the 10x10cm area surrounding the incision. The second value will be the best tissue perfusion relative value (%) observed anywhere in the breast.

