12.3.1 Surgery-related Adverse Events

All adverse events considered by the Investigator to be surgery related will be recorded in the eCRF and classified using the NCI Common Terminology Criteria for Adverse Events (CTCAE) Version 5 criteria for preferred term and severity grading.

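### Reactions to the study dye have no defined place in the eCRF, so the trial cannot systematically report harm from its own six-injection measurement

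*Protocol*

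**What the plan says.** Protocol section 12.3 deals with the dye in one sentence: "Any adverse reactions to the fluorescent Indocyanine Green (ICG) dye will be reported according to local procedures". It then gives a classification, "This study is a non-interventional study", and adds that "No routine adverse event reporting will be undertaken as part of this protocol".

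Section 12.3.1 sets the rule for what enters the database: "All adverse events considered by the Investigator to be surgery related will be recorded in the eCRF", with CTCAE version 5 term and grade. The matching secondary endpoint in section 10.2 is "Incidence, type and severity of surgery-related adverse events, where applicable". Section 13, section 17.2 and the schedule in Appendix 1 keep to the same surgery-related category. On timing, section 12 states that "Surgery-related adverse events will be recorded at each clinic visit from the point of surgery", up to the end of the 30-day follow-up.

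On the dye itself, section 12.2.1 sets an injection at TR1, TR2 and TR3 for the right breast. For the left breast it says that "The surgeon will request that the ICG dye be administered to the patient" at TL1, TL2 and TL3. Section 17.2 describes these injections as the way in which the primary endpoint is measured. Section 11.2 excludes patients with known hypersensitivity to the dye or iodine, or with previous side-effects of the dye.

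**The concern.** The injections are given at times fixed by the protocol, to obtain the study's perfusion readings. Section 7 describes current assessment of flap perfusion as clinical (capillary refill, warmth, serial review), so on the protocol's own account this injection schedule is a study procedure. The exclusion criteria show that a risk is recognised. Even so, no endpoint, eCRF item or attribution category for dye reactions appears in the protocol, and no route is described from a local report to the trial database.

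What is at stake is what the final report can say. Someone planning another study with the same repeated-injection measurement would want to know how many patients reacted. If the protocol is followed as written, a report that mentions no dye reaction could mean that none happened, or that they were handled locally and never entered.

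There is also a link to the analysis set. Section 8.3 counts a patient as evaluable only if all time points were measured on both breasts, and section 14 allows replacement after discontinuation. If a reaction stopped later injections, that patient would leave the evaluable set and the study would hold no dedicated record of why.

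**Working it through.** **Which events reach the eCRF**

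| Event | Rule in the protocol | In the eCRF? |
|---|---|---|
| Judged surgery related | 12.3.1 | Yes, with CTCAE term and grade |
| Dye reaction that the Investigator also judges surgery related | 12.3 and 12.3.1 | Yes, but not identified as due to the dye |
| Dye reaction not judged surgery related | 12.3, local procedures | No stated route |

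Surgery related is not defined. Which of the last two rows applies therefore depends on the individual Investigator. In neither row can the cases be counted afterwards as dye reactions.

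**The denominator.** Section 17.1 gives n = 30 from a 10% difference, SD 25%, one-sided 10% level and 80% power. For a paired test, n = (25 × (1.2816 + 0.8416) / 10)² = 28.2, so 29. Exact noncentral-t power is 79.97% at 29 and 81.0% at 30, so the stated 30 reproduces. The present point does not depend on it beyond using 30 as the number of patients.

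**Number of injections.** 3 time points × 2 breasts = 6 per patient; 6 × 30 = 180. This counts evaluable patients only.

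**What recording would allow.** With no reactions in 30 patients:
- one-sided 95% upper limit: 1 − 0.05^(1/30) = 9.5% of patients
- upper end of a two-sided 95% exact interval: 1 − 0.025^(1/30) = 11.6%

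**Chance of seeing at least one reaction**, 1 − (1 − p)^30. The protocol gives no per-patient rate p, so the values below are assumptions:

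| Assumed p | Chance of at least one in 30 |
|---|---|
| 0.1% | 3% |
| 1% | 26% |
| 5% | 79% |
| 10% | 96% |

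Thirty patients can describe a common reaction. They say very little about a rare one.

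**The case against.** The protocol does not contradict itself here. It makes an explicit choice to send dye reactions to local procedures and collects surgery-related events consistently elsewhere. Section 7 describes the equipment and dye as already in wide surgical use, no objective concerns dye safety, and the study is not sized for it. All of that stands, and it limits the weight of the point. It does not explain why a trial that grades surgery-related events by CTCAE has no defined record for reactions to its own measurement. A statistical analysis plan could not repair this, since it cannot tabulate what was not collected.

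Three stronger readings are tempting, and the protocol does not support them.

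- A reader might infer that dye reactions are barred from the eCRF. They are not. The injections are described under the surgical procedure and given in theatre, so an Investigator could record a reaction under 12.3.1. Section 12.3 also does not say where local reports end up, and section 15 refers to Case Report Form Guidelines that are not shown. What is missing is a systematic record; capture is not ruled out.
- A reader might infer from Appendix 1, where adverse events are marked only at follow-up, that events in theatre are not covered. Section 12 covers events from the point of surgery. The marks show when data are collected, so they leave no gap in the period covered.
- A reader might infer that reactions would go unmanaged. Section 12.3 assigns management of adverse events to local guidelines and reporting of dye reactions to local procedures. The point concerns only what the study records.

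The non-interventional label sits awkwardly beside repeated injections at protocol-set times, but the point does not rest on how the study is classified.

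**Conclusion.** The concern holds in a limited form. The dye sentence in 12.3, read with the eCRF rule in 12.3.1, leaves capture of a dye reaction to chance classification and collects no dye attribution. The trial therefore cannot systematically report reactions to a procedure that it performs six times per patient, 180 times in 30 patients.

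This rests on two readings of the protocol: that no dye item exists in data-collection documents not shown here, and that the injections serve the study's perfusion measurements, as section 17.2 describes. If the Case Report Form Guidelines already include a dye-reaction item, what remains is to bring the protocol text into line with them.

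The primary endpoint and the planned between-breast comparisons do not change. What is lost is a descriptive safety statement, and a modest one: even with complete recording and no events, rates up to about 9.5% of patients would remain compatible with the data. The change is worth making because it is cheap and because the information concerns the study's own procedure.

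**What to change.** In sections 12.3 and 12.3.1, state that any adverse reaction the Investigator attributes to the dye, from the first injection (TR1) to the end of follow-up, is recorded in the eCRF in addition to local reporting. Record the CTCAE version 5 term, the grade, the time point and the dye attribution.

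Report these as a descriptive safety listing per patient, kept separate from the comparisons in sections 10.2 and 17.2. A reaction to an intravenous dye is systemic and cannot be assigned to one breast, so it does not fit those endpoints. The denominator should be all patients who received at least one injection, so that anyone who leaves the evaluable set after a reaction is still counted.

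Marking the surgery columns in Appendix 1 is optional, because section 12 already covers events from the point of surgery.

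Cost: a few eCRF fields and one protocol amendment, which under section 20.3 needs sponsor agreement before submission to the HRA and REC. No extra visits are needed, and no change to dosing or care is implied.

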12.3.1 Surgery-related Adverse Events

All adverse events considered by the Investigator to be surgery related will be recorded in the eCRF and classified using the NCI Common Terminology Criteria for Adverse Events (CTCAE) Version 5 criteria for preferred term and severity grading.

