Surgeons currently employ both intra-operative dissection techniques; therefore, this is not a new intervention; yet, importantly, there is no such novel study design known in the literature.

Therefore, CI with a team of engineers has been working on a device that surgeons can wear that will spread surgeons passively (without fatigue and trauma to their fingers) and at the same time, the extenders will increase reach where fingers can't. This will be an alternative to the retractors.

Whilst seeking funds for the development of the potential solution, it was suggested to gather some objective clinical evidence to demonstrate the difference in trauma caused to the tissues due to both of the existing surgical practices (retractors versus fingers-based).

This prospective case-control study represents an opportunity to compare tissue perfusion during breast mastectomy when using metal retractors versus fingers to lift the tissue. This study does not propose a new surgical technique or use a new instrument.

Differences in tissue perfusion between the two sides in the same patient (so there are no patient confounding factors) will help demonstrate the perceived problem objectively. The outcome of this study will establish the difference in trauma caused to the breast tissues due to current surgical practices, consequently, help improve intra-operative dissection techniques and reduce post-surgery infection and in addition, help to build an evidence-based case for the possible innovation of a new device to aid surgeons during this type of surgery.

In immediate breast reconstruction, the skin envelope with or without nipple must be preserved/spared (skin/nipple sparing mastectomy) after the removal of underlying breast tissue. However, mastectomy removes the dominant blood supply through the breast tissue, so the spared skin needs to survive on smaller blood vessels (capillary network) travelling along the skin's surface.

Tissue perfusion is the blood flow and oxygen supply to tissues, including the skin. Even brief periods of compromised perfusion to the tissue can lead to irreversible harm and complications. Currently tissue flap perfusion for mastectomies (simple, skin and nipple sparing), localised perforator flaps and larger pedicled (LD flap) or anastomotic (DIEP) flaps are assessed by reviewing capillary refill, warmth, and serial patient reviews. There are no additional methods for actual real-time visualisation of the tissue's vasculature.

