8 STUDY DESIGN AND METHODS

8.1 Statement of Design

Patients (n=30) undergoing bilateral mastectomy with immediate breast construction (n=60 breasts) will be invited to take part in this prospective case-control, multi-centre study.

Consenting patients will complete a pre-operative questionnaire and then undergo surgery. In the same patient during the same operative episode, sequential tissue perfusion measurements will be taken as follows:

- First, in the right breast use the finger dissection non-retractor technique for as long as possible before reverting to metal retractors
- Secondly, in the left breast using retractors only throughout the entire procedure

The sequential measurements taken in each breast will allow for the comparison of tissue perfusion between the two different skin lift techniques.

Patients will be blinded to the technique used in each breast.

Following surgery, patients will be followed in order to observe the patient's 30-day postoperative recovery period.

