17 STATISTICS

17.1 The Number of Participants

A likely hypothesis relates to the possibly worse performance of the retractors. Hence, we will use a t-test in order to test the null hypothesis of no difference in perfusion between the two breasts (retractor and non-retractor sides) against the alternative of a 10% difference. With power=80%, a one-sided significance level of 10% and assuming an SD of 25%, the required sample size is n=30 evaluable patients.

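### An adverse event enters the eCRF only if an Investigator who can tell the technique from the side calls it surgery related, so borderline events in a between-breast endpoint could be recorded unevenly

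*Protocol*

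**What the plan says.** Section 12.3.1 of the Protocol sets the rule for entry: "All adverse events considered by the Investigator to be surgery related will be recorded in the eCRF". Events that pass are then coded and graded with CTCAE version 5. Section 12.3 provides no wider route into the study data: "No routine adverse event reporting will be undertaken as part of this protocol". Reactions to the dye are handled through local procedures. Sections 12 and 13 likewise collect only the surgery-related events, and section 12 limits this to the 30-day follow-up. The protocol does not define what makes an event surgery related, and it names no independent or masked assessor.

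The recorded events are an outcome and not only safety documentation. Section 10.2 lists "Incidence, type and severity of surgery-related adverse events, where applicable" among the secondary endpoints compared between the two breasts, and section 17.2 repeats this.

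On masking, section 8.1 says "Patients will be blinded to the technique used in each breast" and mentions nobody else. The same section fixes technique by side: "First, in the right breast use the finger dissection non-retractor technique for as long as possible before reverting to metal retractors" and "Secondly, in the left breast using retractors only throughout the entire procedure". Section 17.1 gives the expected direction: "A likely hypothesis relates to the possibly worse performance of the retractors". Section 7 adds that "CI with a team of engineers has been working on a device that surgeons can wear", meant as an alternative to retractors.

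**The concern.** The number of events in each breast depends on a personal judgement of cause, and that judgement decides whether the event exists in the eCRF at all. The protocol does not say in words that the Investigator is unblinded. It follows from two of its statements: only patients are blinded, and side determines technique in every patient.

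A judgement made with knowledge of the technique, in a study with a stated expectation, can fall differently on the two sides when the event is borderline. The same finding might be recorded as a complication on the left and passed over on the right. No misconduct need be supposed. This is the usual reason for not letting entry of outcome data depend on an opinion about cause.

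What is at stake is the complication part of the secondary objective. With 30 patients there will be few events, so one or two decisions can change the picture. An analysis of the eCRF alone could not restore what was never entered.

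**Working it through.** **The plan's own figure.** The protocol gives no sample size or test for adverse events. Its one calculation (section 17.1) concerns perfusion: difference 10, SD 25, one-sided 10%, power 80%. In the paired form, n = (SD × (z₀.₉₀ + z₀.₈₀) / difference)² = (25 × (1.2816 + 0.8416) / 10)² = 28.2, so 29. With the noncentral t, power is 79.97% at 29 and 81.0% at 30. The stated n=30 reproduces, and nothing below changes it.

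**The chain of statements.**
1. Entry to the eCRF depends on judged relatedness to surgery (12.3.1), and there is no routine reporting of other events (12.3).
2. The events that pass are compared between breasts (10.2, 17.2).
3. Side reveals technique, and masking is stated for patients only (8.1).
4. The expected direction is written down (17.1).

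Together these make uneven recording possible. They do not show that it will happen, or how often.

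**Illustration of size.** The inputs are:
- 30 patients (section 8.3).
- An equal true event rate p in each breast, with the two breasts independent (assumed). I take p = 25%, the infection figure in section 7, and p = 35%, the skin necrosis figure in the control group of the heat-preconditioning trial cited there. Using either as a rate per breast is an assumption.
- All retractor-side events recorded, and a fraction s of finger-side events recorded (assumed).

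Expected recorded events are 30p on the retractor side and 30ps on the finger side. The spurious difference is p(1 − s). For p = 25% and s = 80%, that is 7.5 against 6.0 events, and 0.25 × 0.20 = 5 percentage points.

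The last column is the chance of a nominal one-sided 10% result against retractors. It uses an exact sign test on patients with a recorded event in one breast only. The chance that a patient is discordant is p(1 − ps) towards the retractor side and ps(1 − p) towards the finger side. For p = 25% and s = 80% these are 0.25 × 0.80 = 0.20 and 0.20 × 0.75 = 0.15. The protocol plans no such test, and the 10% level is borrowed from section 17.1 only as a scale.

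| p | s | Events, retractor v finger | Spurious difference (points) | Chance of nominal result |
|---|---|---|---|---|
| 25% | 100% | 7.5 v 7.5 | 0 | 5.8% |
| 25% | 90% | 7.5 v 6.75 | 2.5 | 8.8% |
| 25% | 80% | 7.5 v 6.0 | 5 | 13.0% |
| 25% | 60% | 7.5 v 4.5 | 10 | 26.1% |
| 35% | 100% | 10.5 v 10.5 | 0 | 6.0% |
| 35% | 90% | 10.5 v 9.45 | 3.5 | 10.2% |
| 35% | 80% | 10.5 v 8.4 | 7 | 16.3% |
| 35% | 60% | 10.5 v 6.3 | 14 | 35.8% |

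The first row for each rate is below 10% because the exact test is conservative with few events. At p = 25%, losing 10% of finger-side events keeps the chance below the nominal level, and losing 20% (1.5 events on average) takes it above.

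**The case against.** The filter asks whether an event is related to surgery, not to the retractor. Both breasts have a mastectomy and the same type of reconstruction in one operation. Infection, necrosis or loss of the reconstruction within 30 days would ordinarily be called surgery related on either side. This stands, and it confines the problem to borderline events.

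The obvious alternative causes (smoking, other illness, systemic treatment) belong to the patient and are shared by both breasts. Section 11.2 also removes several one-sided causes, such as certain earlier radiotherapy or surgery on one breast. This stands too. Uneven attribution is possible, but nothing in the protocol makes it likely.

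A reader might infer that an event judged unrelated is lost for good. The documents do not support that. Medical records are source data (section 15.1) and are archived for at least five years (section 16). Re-admission, re-operation, hospital stay and pain in each breast are collected with no judgement of cause (section 13), so a serious event would usually reach the data in another form. The loss concerns the planned eCRF comparison and could in principle be repaired by chart review.

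A reader might also construct a striking example. Suppose seven patients have an event in one breast only, split 5 retractor v 2 finger: one-sided exact p = 29/128 = 0.23. Drop both finger-side events and 5 v 0 gives 1/32 = 0.03. The arithmetic is right, but it assumes that every finger-side event is discarded and every retractor-side event kept, with no planned test behind it. It is a worst case and not an estimate.

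Finally, the endpoint is worded as surgery-related events and the rule collects exactly those, so the protocol does not contradict itself. That is true. The point concerns a stated rule that is more open to bias than it need be.

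**Conclusion.** The concern holds in a limited form. Section 12.3.1 makes a between-breast secondary endpoint depend on a judgement of cause by someone who can know the technique, and the protocol provides no safeguard for borderline events. The effect is probably small, and its size cannot be derived from the document. Under the assumptions shown, finger-side recording of 90% to 60% gives a spurious difference of 2.5 to 10 points at a true rate of 25%, or 3.5 to 14 points at 35%.

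The documents do not show that the comparison is biased towards the study's hypothesis, only that it is exposed to such bias. The primary perfusion endpoint, n=30 and the outcomes collected without a relatedness judgement are untouched. The change is still worth making, because the rule is fixed in the protocol and an analysis plan cannot supply events that were not entered.

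**What to change.** Amend section 12.3.1 so that every breast or wound event in either breast from surgery to day 30 is entered in the eCRF with its side, whatever its judged cause. The list should contain at least infection, skin necrosis, and loss of the implant or reconstruction. Keep the Investigator's opinion on relatedness as a separate field. Compare all such events between breasts first and the related subset second, and bring the wording of the synopsis and of sections 10.2, 12, 13 and 17.2 into line.

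The cost is a protocol amendment, a relatedness field and a few extra entries for 30 patients. Some events that have nothing to do with technique will be counted and add a little noise. The related subset remains available, and no patient's care changes.

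This removes the filter on entry only. Events would still be detected and CTCAE-graded by staff who can know the technique, and the protocol and the report should state that as a limitation.
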